9.0 ADMINISTRATIVE AND ETHICAL CONSIDERATIONS

9.1 Regulatory and Ethical Compliance

This protocol was designed and will be conducted and reported in accordance with the International Conference on Harmonization (ICH) Harmonized Tripartite Guidelines for Good Clinical Practice, the Declaration of Helsinki, and applicable federal, state, and local regulations.

9.2 DUHS Institutional Review Board and DCI Cancer Protocol Committee

The protocol, informed consent form, advertising material, and additional protocol-related documents must be submitted to the DUHS Institutional Review Board (IRB) and DCI Cancer Protocol Committee (CPC) for review. The study may be initiated only after the Principal Investigator has received written and dated approval from the CPC and IRB.

The Principal Investigator must submit and obtain approval from the IRB for all subsequent protocol amendments and changes to the informed consent form. The CPC should be informed about any protocol amendments that potentially affect research design or data analysis (i.e. amendments affecting subject population, inclusion/exclusion criteria, agent administration, statistical analysis, etc.).

The Principal Investigator must obtain protocol re-approval from the IRB within 1 year of the most recent IRB approval. The Principal Investigator must also obtain protocol re-approval from the CPC within 1 year of the most recent IRB approval, for as long as the protocol remains open to subject enrollment.

9.3 Informed Consent

The informed consent form must be written in a manner that is understandable to the subject population. Prior to its use, the informed consent form must be approved by the IRB.

The Principal Investigator or authorized key personnel will discuss with the potential subject the purpose of the research, methods, potential risks and benefits, subject concerns, and other study-related matters. This discussion will occur in a location that ensures subject privacy and in a manner that minimizes the possibility of coercion. Appropriate accommodations will be made available for potential subjects who cannot read or understand English or are visually impaired. Potential subjects will have the opportunity to contact the Principal investigator or authorized key personnel with questions, and will be given as much time as needed to make an informed decision about participation in the study.

Before conducting any study-specific procedures, the Principal Investigator must obtain written informed consent from the subject or a legally acceptable representative. The original informed consent form will be stored with the subject's study records, and a copy of the informed consent form will be provided to the subject. The Principal Investigator is responsible for asking the subject whether the subject wishes to notify his/her primary care physician about participation in the study. If the subject agrees to such notification, the Principal Investigator will inform the subject's primary care physician about the subject's participation in the clinical study.

9.4 Study Documentation

Study documentation includes but is not limited to source documents, case report forms (CRFs), monitoring logs, appointment schedules, study team correspondence with sponsors or regulatory bodies/committees, and regulatory documents that can be found in the DCI-mandated “Regulatory Binder”, which includes but is not limited to signed protocol and amendments, approved and signed informed consent forms, FDA Form 1572, CAP and CLIA laboratory certifications, and clinical supplies receipts and distribution records.

Source documents are original records that contain source data, which is all information in original records of clinical findings, observations, or other activities in a clinical trial necessary for the reconstruction and evaluation of the trial. Source documents include but are not limited to hospital records, clinical and office charts, laboratory notes, memoranda, subjects' diaries or evaluation checklists, pharmacy dispensing records, recorded data from automated instruments, copies or transcriptions certified after verification as being accurate copies, microfiches, photographic negatives, microfilm or magnetic media, x-rays, subject files, and records kept at the pharmacy, at the laboratories and at medico-technical departments involved in the clinical trial. When possible, the original record should be retained as the source document. However, a photocopy is acceptable provided that it is a clear, legible, and an exact duplication of the original document.

A case report form (CRF) (please indicate whether a paper or electronic CRF will be used) will be the primary data collection document for the study. The CRFs will be updated within two weeks of acquisition of new source data. Only approved study staff (data coordinators), are permitted to make entries, changes, or corrections in the CRF. For paper CRFs, errors will be crossed out with a single line, and this line will not obscure the original entry. Changes or corrections will be dated, initialed, and explained (if necessary). The Principal Investigator or authorized key personnel will maintain a record of the changes and corrections. For electronic CRFs, an audit trail will be maintained by the electronic CRF management system (please indicate what eCRF management system is being used).

9.5 Privacy, Confidentiality, and Data Storage

The Principal Investigator will ensure that subject privacy and confidentiality of the subject's data will be maintained. Research Data Security Plans (RDSPs) will be approved by the appropriate institutional Site Based Research group.

To protect privacy, every reasonable effort will be made to prevent undue access to subjects during the course of the study. Prospective participants will be consented in an exam room where it is just the research staff, the patient and his family, if desired. For all future visits, interactions with research staff (study doctor and study coordinators) regarding research activities will take place in a private exam room. All research related interactions with the participant will be conducted by qualified research staff who are directly involved in the conduct of the research study.

To protect confidentiality, subject files in paper format will be stored in secure cabinets under lock and key accessible only by the research staff. Subjects will be identified only by a unique study number and subject initials. Electronic records of subject data will be maintained using a dedicated database (Microsoft Access), which is housed in an encrypted and password-protected DCI file server (\\cancerlan6\adulrbmt_pro). Access to electronic databases will be limited to staff of the division of Cellular Therapy. The security and viability of the IT infrastructure will be managed by the DCI and/or Duke Medicine.

Upon completion of the study, research records will be archived and handled per DUHS HRPP policy.

Subject names or identifiers will not be used in reports, presentations at scientific meetings, or publications in scientific journals.

9.6 Data and Safety Monitoring

Data and Safety Monitoring will be performed in accordance with the DCI Data and Safety Monitoring Plan. For a more detailed description of the DSMP for this protocol, refer to Section 8.

9.7 Protocol Amendments

All protocol amendments must be initiated by the Principal Investigator and approved by the IRB prior to implementation. IRB approval is not required for protocol changes that occur to protect the safety of a subject from an immediate hazard. However, the Principal Investigator must inform the IRB and all other applicable regulatory agencies of such action immediately.

Though not yet required, the CPC should be informed about any protocol amendments that potentially affect research design or data analysis (i.e. amendments affecting subject population, inclusion/exclusion criteria, agent administration, etc.).

9.8 Records Retention

The Principal Investigator will maintain study-related records for the longer of a period of:

- at least two years after the date on which a New Drug Application is approved by the FDA (if an IND is involved)
- at least two years after formal withdrawal of the IND associated with this protocol (if an IND is involved)
- at least six years after study completion (Duke policy)

Appendix I: Toxicity Forms

Table 8: Grading GVHD

Stage	Skin	Liver	Gut
1	Rash on <25% of skin	Bilirubin 2.0-3.0 mg/dl	Diarrhea >500 ml/day or persistent nausea
2	Rash on 25-50% of skin	Bilirubin 3.1-6.0 mg/dl	Diarrhea >1000 ml/day
3	Rash on >50% of skin	Bilirubin 6.1-15.0 mg/dl	Diarrhea >1500 ml/day
4	Generalized erythroderma with bullous formation	Bilirubin >15 mg/dl	Severe abdominal pain with or without ileus
Grade			
I	Stage 1-2	None	None
II	Stage 3 or	Stage 1 or	Stage 1
III	-	Stage 2-3 or	Stage 2-4
IV	Stage 4 or	Stage 4	-

Common Toxicity Criteria Version 4.0

<http://ctep.cancer.gov/reporting/ctc.html>

Appendix II

ECOG PERFORMANCE STATUS SCALE

ECOG Scale*	ECOG Description
0	Fully active, able to carry on all pre-disease activities without restriction.
1	Restricted in physically strenuous activity but ambulatory and able to carry out work of a light or sedentary nature e.g. light house work office work.
2	Ambulatory and capable of all self care but unable to carry out any work activities. Up and about more than 50% of waking hours
3	Capable of only limited self care, confined to bed or chair more than 50% of waking hours
4	Completely disabled. Cannot carry on any self care. Totally confined to bed or chair
Dead	

Appendix III: Patient Eligibility Checklist

Desired answer	Answer	Date determined	Eligibility Criteria
Inclusion criteria			
yes			Patients with hematologic diseases who have undergone allogeneic transplantation, using a 7-8/8 HLA-matched related or unrelated donor or 4-6/8 HLA-matched related donor. This may include patients with a mixed chimeric state or disease persistence or at high risk of relapse (these are patients who do not fit exclusionary principle 3 below).
yes			Performance status must be ECOG PS 0, 1, or 2
yes			Donor cellular engraftment of at least 2.5%
yes			<Grade 2 acute GVHD at time of the first NK cell-enriched DLI. Patients with treated acute GVHD must be on a stable dose of therapy (no increase in immunosuppressive therapy for the 2 weeks before planned NK cell-enriched DLIs). The dosage/level of immunosuppressive therapy at the time of NK-DLIs should be no greater than 20 mg/kg of prednisone daily or mycophenolate 500 mg bid daily or cyclosporine with a target level of 200 ng/mL or tacrolimus with a target level of 10 ng/ml.
yes			Estimated survival of at least 8 weeks
yes			Age of \geq 18 years
Yes			Females of childbearing potential should have a negative serum beta-HCG test within 48 hours of beginning DLI and/or DUK-CPG-01 unless contraception is used after initial testing.
Yes			Males must agree to use a medically acceptable form of birth control in order to be in this study and for 3 months after infusion
Exclusion criteria			
no			Pregnant or lactating women
no			Patients with other major medical or psychiatric illnesses, which the treating physician feels, could seriously compromise tolerance to this protocol.
no			Patients likely to have a significantly better durable response to allogeneic transplant alone (better than 60% progression free longer than 2 years) includes: those with uncomplicated myeloproliferative diseases or hemoglobinopathies with over 50% T cell subset engraftment (assessed around 100 days post transplant); It is not anticipated that any such patients would be transplanted within our program, however those in first remission AML patients with good risk standard genetics or normal genetics with only either NPM1 or CEBPA mutations, first chronic phase CML without kinase gene mutations, follicular lymphoma patients in first remission who only required 1 regimen to attain remission all would be excluded from this protocol.

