2. To evaluate the one-year progression-free survival rates in patients receiving NK cell-enriched DLI administered with a Toll-like receptor 9 (TLR9) ligand, DUK-CPG-001, from a 7-8/8 HLA-matched related or unrelated donor or 4-6/8 HLA-matched related donor following allogeneic stem cell transplantation
3. To evaluate the rates of unacceptable toxicity of using NK cell-enriched DLI administered alone from a 7-8/8 HLA-matched related or unrelated donor or 4-6/8 HLA-matched related donor following allogeneic stem cell transplantation.
4. To evaluate the rates of unacceptable toxicity of using NK cell-enriched DLI administered with TLR9 ligand, DUK-CPG-001, from a 7-8/8 HLA-matched related or unrelated donor or 4-6/8 HLA-matched related donor following allogeneic stem cell transplantation.

The secondary objectives of this study are:

1. To evaluate the recovery of immune cell populations pre and post infusion in patients receiving NK cell-enriched DLI administered alone or administered with TLR9 ligand, DUK-CPG-001.
2. To evaluate the immune function with antigen specific recovery with Elispot, Immunoscope, and flow-cytometric cytokine assay, and functional NK lysis assay, pre and post infusion in patients receiving NK cell-enriched DLI administered alone or administered with TLR9 ligand, DUK-CPG-001.

Patient population

Patients who have undergone an allogeneic transplantation, using a 7-8/8 HLA-matched related/unrelated donor (Cohort A) or 4-6/8 HLA-matched related donor (Cohort B). Specific inclusion and exclusion criteria are detailed in 3.0 Eligibility criteria.

Number of patients

A total of 50 patients (25 patients in each arm) will be enrolled in Cohort A, and 50 patients (25 patients in each arm) will be enrolled in Cohort B.

Study design and methodology

This is a randomized, parallel phase II study to evaluate the rates of progression-free survival and unacceptable toxicity in patients receiving NK cell-enriched DLIs when administered alone or administered with the TLR9 agonist, DUK-CPG-001, from a 7-8/8 HLA-matched related/unrelated donor (Cohort A) or 4-6/8 HLA-matched related donor (Cohort B) following allogeneic stem cell transplantation. Randomization will be stratified for disease types (myeloid versus lymphoid malignancies). Primary endpoints are analyzed separately in Cohort A and B.

Cohort A: 8/8 HLA-matched (related or unrelated) donor
("NK cell enriched-DLI only" arm or "NK cell enriched-DLI + DUK-CPG-001" arm)

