3 ELIGIBILITY CRITERIA

3.1 Inclusion criteria

1. Patients with hematologic diseases who have undergone an allogeneic transplantation, using a 7-8/8 HLA-matched related or unrelated donor or 4-6/8 HLA-matched related donor. This may include patients with a mixed chimeric state or disease persistence or at high risk of relapse (these are patients who do not fit exclusionary principle 3 below).
2. Performance status must be ECOG PS 0, 1, or 2.
3. Donor cellular engraftment of at least 2.5%.
4. < Grade 2 acute GVHD at time of the first NK cell-enriched DLI. Patients with treated acute GVHD must be on a stable dose of therapy (no increase in immunosuppressive therapy for the 2 weeks before planned NK cell-enriched DLIs). The dosage/level of immunosuppressive therapy at the time of NK-DLIs should be no greater than 20mg of prednisone daily or mycophenolate 500 mg bid daily or cyclosporine with a target level of 200 ng/mL or tacrolimus with a target level of 10 ng/ml.
5. Estimated survival of at least 8 weeks.
6. Age of \geq 18 years.
7. Females of childbearing potential should have a negative serum beta-HCG test within 48 hours of beginning DLI and/or DUK-CPG-01 unless contraception is used after initial testing. *A female of childbearing potential (FCBP) is a sexually mature female who: 1) has not undergone a hysterectomy or bilateral oophorectomy; or 2) has not been naturally postmenopausal for at least 24 consecutive months (i.e., has had menses at any time in the preceding 24 consecutive months).*

8. Males must agree to use a medically acceptable form of birth control in order to be in this study and for 3 months after infusion

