3.2 Exclusion criteria

1. Pregnant or lactating women.
2. Patients with other major medical or psychiatric illnesses, which the treating physician feels, could seriously compromise tolerance to this protocol.
3. Patients likely to have a significantly better durable response to allogeneic transplant alone (better than 60% progression free longer than 2 years) includes: those with myeloproliferative diseases or hemoglobinopathies with over 50% T cell subset engraftment (assessed around 100 days post transplant); It is not anticipated that any such patients would be transplanted within our program, however but those in first remission AML patients with good risk standard genetics or normal genetics with either NPM1 or CEBPA mutations, first chronic phase CML without kinase gene mutations, follicular lymphoma patients in first remission who only required 1 regimen to attain remission all would be excluded from this protocol.

3.3 HLA 4-8/8 matched related donor inclusion/exclusion criteria (criterion below are recommended but may evolve to follow current program standards) to be completed within 30 days of apheresis per standard guidelines

1. Adult donors must be an HLA 4-8/8 match with the patient
2. Potential donors under the age of 18 must have a single patient exemption approved by the IRB.
3. Donor must not have any medical condition which would make apheresis more than a minimal risk, and should have the following:
 - (a) Family members will be considered for donation if they do not have a history of known cardiac problem and do not have abnormal cardiac findings by physical examination. Those with a history of cardiac problems or abnormal cardiac findings by physical examination should undergo a stress evaluation or be evaluated by a cardiologist and deemed eligible to donate.
 - (b) Documented bilirubin and hepatic transaminases of $\leq 2.5 \times$ ULN,
 - (c) Documented adequate hematologic parameters including a hematocrit $> 35\%$ for males and 33% for females, white blood cell count of $\geq 3,000$, and platelets $\geq 80,000$.
 - (d) FACT labs and final test results available prior to infusion into the patient (copy of labs included in appendices). In the second donation from the donor, the FACT labs must be redrawn within 30 days of initiation of apheresis. Positive serologies are not repeated as they remain positive for lifetime.

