4.4 Patient NK cell infusion and CpG administration plan

This treatment regimen may be administered on an outpatient basis.

4.4.1 NK cell-enriched DLI:

The target cell dose for NK cell-enriched DLI will be as many cells as can be collected with less than 0.5×10^6 CD3+ CD56- cells/kg patient weight in the 4-6/8 HLA-matched related setting and 1×10^6 CD3+ CD56- cells/kg patient weight in the 7-8/8 HLA-matched related or unrelated setting. The first NK cell-enriched DLI will be administered between one to six months post-transplant. The second NK cell-enriched DLI will be administered one to three months post the first infusion, in patients who have < grade II aGVHD at the time of infusion and have not had unacceptable toxicities (see 6.2.1 Definition of unacceptable toxicity) that are at least possibly related to the previous DLI and resolved to grade 1 or less. The second DLI will NOT be administered in patient with \geq grade III aGVHD at the time of infusion or unacceptable toxicities at least possibly related to the first infusion. If patients have GVHD and were on immunosuppressive therapy at study entry, patients will continue on their stable dose of immunosuppressive agents started for therapy of acute GVHD before the NK cell-enriched DLI, and will not taper until at least 6 weeks following the each NK cell-enriched DLI (unless disease progression or patient toxicity from the agents requires earlier taper). The donor NK cells will be infused over 30 minutes. Diphenhydramine 25 mg iv or po, and Acetaminophen 650 mg po will be used prior to each reinfusion, unless there is a history of allergy or contraindication in the patient, in which case hydrocortisone 50mg IV will be used.

These cells are infused into the patient via a peripheral intravenous line or central line. If signs of GVHD occur after NK cell-enriched DLI, immunosuppressive agents (prednisone, cyclosporine, tacrolimus and/ or mycophenolate preferred first choices) may be started.

4.42 Adverse effect of NK cell-enriched DLI:

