5.0 PATIENT REGISTRATION

All patients must be registered with the study coordinator and data coordinator. The eligibility checklist must be complete and the IRB approved consent form signed before any protocol therapy may be started on the patient or donor.

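### The prednisone limit at the time of the NK-DLIs is 20 mg daily in Section 3.1 but 20 mg/kg daily on the Appendix III eligibility checklist, and the two texts must be reconciled

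*Combined protocol and SAP*

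**What the plan says.** Section 3.1 (Inclusion criteria), item 4 limits immunosuppressive therapy at the time of the NK cell-enriched DLIs. For prednisone and mycophenolate the limit reads "no greater than 20mg of prednisone daily or mycophenolate 500 mg bid daily".

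The Appendix III Patient Eligibility Checklist restates this criterion, with yes as the desired answer. There the limit reads "no greater than 20 mg/kg of prednisone daily or mycophenolate 500 mg bid daily".

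Section 5.0 makes a checklist a condition of treatment: "The eligibility checklist must be complete and the IRB approved consent form signed before any protocol therapy may be started". It does not name Appendix III, but no other patient eligibility checklist appears in the document.

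The only other mention of prednisone is in Section 4.4.1, for GVHD that appears after the infusion: "immunosuppressive agents (prednisone, cyclosporine, tacrolimus and/ or mycophenolate preferred first choices) may be started". No dose is given there.

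The Protocol Summary, under Patient population, points the reader to the body of the protocol: "Specific inclusion and exclusion criteria are detailed in 3.0 Eligibility criteria".

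**The concern.** One criterion has two values that cannot both apply. The difference is one of units, a fixed daily dose against a dose per kilogram, so it is not a matter of rounding or phrasing. One of the two values sits on the form that is completed before a patient may start protocol therapy.

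Staff working from Section 3.1 and staff working from the checklist could reach opposite decisions on the same patient. An enrolment could be correct by the checklist and a deviation from Section 3.1, or the reverse, and a monitor would have no written rule for deciding which. What is at stake is consistent application of an entry limit on immunosuppression at the time of a donor-cell infusion.

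**Working it through.** **Step 1. Is it the same criterion?** The elements side by side:

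| Element | Section 3.1, item 4 | Appendix III |
|---|---|---|
| Acute GVHD at first DLI | below grade 2 | below grade 2 |
| Increase in immunosuppression, prior 2 weeks | none | none |
| Prednisone limit | 20 mg daily | 20 mg/kg daily |
| Mycophenolate limit | 500 mg bid | 500 mg bid |
| Cyclosporine target level | 200 ng/mL | 200 ng/mL |
| Tacrolimus target level | 10 ng/mL | 10 ng/mL |

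Five of the six elements agree. These are two statements of one rule, not separate rules for different situations. Both are current text, and conversion from PDF is unlikely to have inserted a per-kilogram unit.

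**Step 2. Does anything in the document settle it?**

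- Prednisone is named in three places. Two give limits that disagree; the third, Section 4.4.1, gives no dose.
- The Protocol Summary says the criteria are in Section 3.0 but does not say what happens if the checklist differs.
- The one explicit precedence statement is in the title of Appendix V. It ranks the full protocol above the schedule-of-events chart and is confined to that chart.

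So nothing resolves the difference.

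**Step 3. How far apart are the limits?** For body weight W in kg:

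ratio = (20 mg/kg × W kg) / 20 mg = W

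The document gives no patient weights, so W is an assumption:

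| Assumed W (kg) | 20 mg/kg as a daily dose | Ratio to 20 mg | Daily doses on which the texts disagree |
|---|---|---|---|
| 50 | 1,000 mg | 50 | above 20 mg, up to 1,000 mg |
| 70 | 1,400 mg | 70 | above 20 mg, up to 1,400 mg |
| 100 | 2,000 mg | 100 | above 20 mg, up to 2,000 mg |

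A dose in the last column meets the Appendix III limit and fails the Section 3.1 limit. A dose of 20 mg or less meets both.

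**Step 4. Is this the only mismatch between checklist and body?** No. Other differences, all secondary and not a complete list:

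- Exclusion criterion 3. Section 3.2 has "those with myeloproliferative diseases or hemoglobinopathies with over 50% T cell subset engraftment"; Appendix III has "those with uncomplicated myeloproliferative diseases or hemoglobinopathies with over 50% T cell subset engraftment". For AML, Section 3.2 has "normal genetics with either NPM1 or CEBPA mutations", where Appendix III inserts the word *only* before the two mutations.
- Donor pregnancy test. Section 3.3, item 4 allows 48 hours before apheresis, with an exception for contraception. Appendix IV allows 1 week, without that exception.
- Donor bilirubin and transaminases. Section 3.3, item 3(b) has at most 2.5 × ULN; Appendix IV has below 2.5 × ULN.

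**The case against.** The best defence is that the protocol body is evidently the source text and the appendices are derived from it. The Protocol Summary sends the reader to Section 3.0 for the criteria, and the Appendix V title puts the full protocol above its own chart. On that reading Section 3.1 governs and the checklist contains a transcription slip that a clinician would notice. This has some force as an inference about drafting, but it is not a rule. The precedence statement covers one chart, nothing similar is attached to Appendix III, and Section 5.0 makes completion of the checklist, not a reading of Section 3.1, the stated condition for starting therapy.

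Three further points limit how much can be claimed:

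- The 50- to 100-fold figure describes the gap between two printed limits at assumed weights. It does not predict the doses patients will be taking.
- The document does not state the purpose of the immunosuppression limit. It stands within the acute GVHD criterion and applies at infusion, so it plausibly bears on safety, but the protocol does not spell that out.
- The donor differences are minor. The Section 3.3 heading calls those criteria recommended and open to change, and the liver-test difference matters only at exactly 2.5 × ULN.

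All three stand as limits on scope. None removes the contradiction in the prednisone limit.

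**Conclusion.** The concern holds. The same eligibility criterion carries two prednisone limits that differ by a factor equal to body weight in kg, which is 50- to 100-fold if weights run from 50 to 100 kg. The contradiction itself follows from reading the two passages and needs no assumption; only the size in milligrams depends on assumed weights.

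The practical effect is confined to patients who meet the rest of the criterion and whose dose lies between the two limits. Their number is not known. The primary analyses, decision boundaries and sample size are not affected by the point as stated.

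It must still be corrected, because one of the conflicting values is on the only patient eligibility checklist and a completed checklist is required before treatment. The other checklist differences would not justify that rating by themselves; they support a wider check.

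**What to change.** 1. The investigator should reconcile Section 3.1, item 4 with Appendix III so that both state one confirmed prednisone limit in the same units. Which limit is right is for the investigator to establish.
2. If any patients are already registered (the document gives no accrual status), check their prednisone dose at the time of each NK-DLI against the confirmed limit and document any discrepancy.
3. In the same amendment, compare Appendices III and IV with Section 3 line by line and reconcile the remaining differences, including the exclusion-criterion wording, the donor pregnancy-test window and exception, and the donor liver-test limit.

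The cost is one amendment, one comparison of two short checklists, and a brief check of registered patients if there are any. Hypotheses, sample size and stopping boundaries do not change.
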